10.3.4.5. Laboratory Analyses

Laboratory safety measurements will be summarized. For continuous (numeric) laboratory analytes, the change from baseline by visit will be summarized as detailed in Section 10.3.1. Change from baseline to endpoint (LOCF) will be analyzed using an ANOVA on the ranks with treatment as a fixed effect unless otherwise specified. For subjective (qualitative) laboratory analytes, counts and percentages of patients with normal and abnormal values will be analyzed using Fisher's exact test.

Shift tables of the change from baseline value to the most extreme postbaseline value and from baseline to Week 52 for selected analytes using clinically meaningful thresholds will be summarized.

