5.2. Determination of Sample Size

Assuming a screen failure rate of 40%, approximately 3000 patients will need to be screened to attain approximately 1800 patients randomized to the 3 treatment groups (600 patients/group) in a 1:1:1 ratio for dulaglutide 4.5 mg, 3.0 mg, and 1.5 mg. Assuming 15% dropout rate, this will result in approximately 510 patients per arm completing 36 weeks of treatment (the primary endpoint).

The aforementioned sample size provides $\geq 80\%$ power to demonstrate superiority of at least 1 of the investigational dulaglutide doses (4.5 mg or 3.0 mg) to dulaglutide 1.5 mg with respect to the primary endpoint (change from baseline in HbA1c) at Week 36 (Visit 9). This sample size is calculated based on the assumption that there is a treatment difference (for either investigational dose) in HbA1c change from baseline of approximately -0.22%, a standard deviation (SD) of 1.1%, and a 2-sided alpha of 0.05.

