The treatment-regimen estimand is included as primary at the request of the US Food and Drug Administration (FDA). The efficacy estimand will be considered primary for all other purposes, and will be applied to all efficacy outcomes unless otherwise specified to demonstrate the effect of treatment and avoid confounding effects with other antihyperglycemic agents.

Each of the estimands will be tested at the full significance level of 0.05.

Analyses of safety parameters will be conducted for the Safety Population unless otherwise specified.

Countries with fewer than 10 randomized patients will be pooled for statistical analyses. Pooled country will be employed for all formal statistical model-based analyses as a block factor unless otherwise denoted.

Unless otherwise specified, all tests of treatment effects will be conducted at a 2-sided alpha level of 0.05, and confidence intervals (CIs) will be calculated at 95%, 2-sided. All tests of interactions between treatments and factors of interest will be conducted at a 2-sided alpha level of 0.10. Multiplicity adjustment will be performed among the hypotheses related to the primary and secondary efficacy endpoints.

The baseline visit will be Visit 3. For all variables, including HbA1c, if baseline data are not available or are missing, the last nonmissing measurement taken up to the first dosing date/time will be used for the baseline measurement. The efficacy measure for the primary analysis is defined as the change from baseline in HbA1c to Week 36 (Visit 9).

For all statistical analyses, missing data will be treated as missing at random for all analyses unless otherwise specified.

The treatment groups mentioned in this document are based on the randomized treatment groups: dulaglutide 4.5 mg, dulaglutide 3.0 mg, and dulaglutide 1.5 mg.

All efficacy and safety data will be summarized by each treatment group at each scheduled visit unless otherwise indicated. Dulaglutide 1.5 mg will serve as the reference treatment for treatment comparison in all efficacy analyses unless otherwise specified.

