The efficacy estimand analysis for a longitudinal continuous variable will employ a mixed-model repeated measure (MMRM) using restricted maximum likelihood to obtain model estimates with Kenward-Roger option to estimate denominator degrees of freedom. The model will include factors for treatment, pooled country, visit, treatment-by-visit interaction, and the baseline as a covariate. The observed margins option will be used in the LSMEANS statement whenever this option is allowed. For analyses of body weight and FSG, the baseline HbA1c strata ($\geq 8.5\%$ [69 mmol/mol] and $< 8.5\%$) will be added in this model as a fixed effect. An unstructured covariance structure will be used to model the within-patient errors. If this model fails to converge, the following covariance structures will be tested in order:

- toeplitz with heterogeneity
- autoregressive with heterogeneity, by visit
- compound symmetry with heterogeneous variances, by visit
- toeplitz
- autoregressive
- compound symmetry without heterogeneous variances, by visit
- compound symmetry

The first covariance structure that converges will be used.

The analysis model for nonlongitudinal continuous variables will be analysis of covariance (ANCOVA) coupled with imputation for missing endpoints unless otherwise noted.

For continuous laboratory measurements for safety, an analysis of variance (ANOVA) on ranks on change from baseline using last observation carried forward (LOCF) at Week 36 (Visit 9) and/or Week 52 (Visit 11) will be used with treatment as a fixed effect.

For all continuous measures, summary statistics will include number of patients, mean, SD, median, minimum, and maximum for both the actual and change from baseline values at each scheduled visit for each treatment unless otherwise specified. Least-squares means (LS means) and standard errors derived from the model will also be displayed for the change from baseline values at each scheduled visit for each treatment. Treatment comparisons will be displayed showing the treatment difference LS means and the 95% CIs between each investigational dulaglutide dose and dulaglutide 1.5 mg (treatment differences) at the same visit, along with the corresponding p-values.

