6.10.1.2.9. Acute Renal Events

Summaries of all treatment-emergent renal safety events will be generated by PT with decreasing frequency by treatment separately for acute renal failure and chronic renal failure. To examine AEs indicating decrease in renal function, the SMQ for Acute Renal Failure and an LSC for chronic renal failure events will be used to search the clinical trial database for events of interest.

A summary and analysis using LOCF will be provided for renal functional laboratory measures: estimated glomerular filtration rate (eGFR) using Chronic Kidney Disease-Epidemiology Collaboration (CKD-EPI); eGFR using CKD-EPI cystatin-C equation (Inker et al. 2012); eGFR using CKD-EPI creatinine-cystatin-C equation (Inker et al. 2012); and creatinine, urine albumin/creatinine ratio (UACR), by treatment. The ANOVA model will be fit with treatment as a fixed effect on the ranked LOCF change from baseline data.

The minimum eGFR (CKD-EPI) value and the maximum creatinine, and UACR will be used for baseline and postbaseline calculations to generate the shift table. The shift table will use eGFR cutoffs (<30 , 30 to <60 , 60 to <90 , and ≥ 90 mL/min/1.73 m²); creatinine cutoffs ($\leq 1 \times$ upper limit of normal [ULN], $>1 \times$ and $\leq 2 \times$ ULN, $>2 \times$ and $\leq 4 \times$ ULN, and $>4 \times$ ULN); and UACR cutoffs (<30 , ≥ 30 , and ≤ 300 , and >300 mg/g).

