6.10.4. Clinical Laboratory Evaluation

Analyses of eGFR, creatinine, and UACR are described in Section 6.10.1.2.9. For other laboratory safety parameters, summaries will be provided in this section. For continuous (numeric) laboratory analytes, including serum lipid parameters (total cholesterol, high-density lipoprotein cholesterol, low-density lipoprotein cholesterol, very-low density lipoprotein cholesterol, and triglycerides), the rank of the change from baseline to endpoint (Week 36 [Visit 9] for primary DBL, Week 52 [Visit 11] for final DBL) will be analyzed as detailed in Section 6.1. For qualitative laboratory analytes, the numbers and percentages of patients with normal and abnormal values will be summarized by treatment.

Each pancreatic enzyme (pancreatic amylase [p-amylase] and lipase) and the maximum postbaseline value will be summarized by treatment in a shift table using $>1 \times \text{ULN}$ and $\geq 3 \times \text{ULN}$ separately for the Safety Population, Safety Population with normal baseline value, and Safety Population with baseline value $>1 \times \text{ULN}$.

An MMRM with pooled country, baseline HbA1c strata, treatment, visit, and treatment-by-visit interaction as fixed effects will be fit to analyze each pancreatic enzyme up to Week 52 (Visit 11). In this model, the log-transformed (post first dose measure/baseline measure) will be

the response variable, and log-transformed baseline measure will be used instead of baseline measure. The variance-covariance structure selection is detailed in Section 6.1.

An ANCOVA model for Week 36 (Visit 9) measurement using LOCF will be fit with the same model as the aforementioned MMRM but removing all terms containing visit.

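### UACR is tested only on ranks of its absolute change from baseline; a log-ratio analysis, already planned for amylase and lipase, would give an effect size and, under stated assumptions, more power

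*SAP*

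**What the plan says.** SAP 6.10.1.2.9 (Acute Renal Events) groups three eGFR equations, creatinine and UACR under one method: "The ANOVA model will be fit with treatment as a fixed effect on the ranked LOCF change from baseline data". The model has no baseline term. A shift table is also planned for UACR. It compares maximum baseline with maximum postbaseline values in three categories: below 30, 30 to 300, and above 300 mg/g.

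No other model-based analysis of UACR is planned. SAP 6.10.4 sends the reader back: "Analyses of eGFR, creatinine, and UACR are described in Section 6.10.1.2.9". The rank method is the general default for continuous safety laboratory measures in SAP 6.1 and in Protocol 10.3.4.5. The general rule in SAP 6.1 is that, unless otherwise specified, "all tests of treatment effects will be conducted at a 2-sided alpha level of 0.05".

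The SAP does not label the change as absolute, but that is its plain reading. Table GBGL.3, for ECGs, lists change and percent change from baseline as separate quantities.

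For pancreatic amylase and lipase SAP 6.10.4 takes a different route: "the log-transformed (post first dose measure/baseline measure) will be" the response in a repeated-measures model, with log baseline as covariate.

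**The concern.** Ranks protect against outliers, but they order whatever quantity they are given. A patient who halves from 10 to 5 mg/g has a change of -5. A patient who falls 5%, from 300 to 285 mg/g, has a change of -15. The small proportional fall therefore ranks as the larger one. With a wide spread of baselines, patients with high values tend to fill both ends of the ranking because of where they started. Patients with low values crowd the middle, and much of the information on their proportional change is lost.

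Two things are at stake. If dose acts proportionally, the planned test may be less sensitive than a log-scale test of the same data. And whatever the power, a rank ANOVA cannot say how large a difference between doses the data exclude. Acute renal events are an adverse event of special interest, and the secondary safety objective is to compare each higher dose with 1.5 mg. A ratio with a confidence interval serves that comparison better than a rank p-value. The shift table does not supply it: a maximum that moves from 8 to 25 mg/g, about threefold, stays in the lowest category.

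**Working it through.** **Inputs from the documents.** 600 patients per arm and 15% dropout (SAP 5.2), so 600 × 0.85 = 510 per arm; two-sided alpha 0.05 (SAP 6.1). The only stated power is for HbA1c. It reproduces: 0.22 / (1.1 × √(2/510)) = 3.19, and Φ(3.19 − 1.96) = 0.89 per comparison, or Φ(3.19 − 2.24) = 0.83 at the split alpha of 0.025. Both agree with the stated figure of at least 80%. No power is stated for UACR.

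**Inputs assumed, because the documents give none.** Log-normal UACR; SD of baseline log-UACR 0.8 to 1.8; residual SD on the log scale 0.8; a uniform dose ratio between about 0.84 and 1.20; regression to the mean of 0 or 0.2 on the log scale.

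**Closed-form check of the log-ratio test.** For a dose ratio of 0.869, ln(0.869) = −0.140. The standard error is 0.8 × √(2/510) = 0.0501, so z = 2.80 and power = Φ(2.80 − 1.96) = 0.80. Simulation gives 81%.

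**Scale alone** (simulation, three arms, 4.5 mg versus 1.5 mg, 510 per arm, no regression to the mean; Monte Carlo error about 1 to 2 points):

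| Baseline log-SD | Fall, ratio 0.869: planned / log ratio | Gap | Rise, ratio 1.151: planned / log ratio | Gap |
|---|---|---|---|---|
| 0.8 | 71% / 81% | 10 | 71% / 79% | 8 |
| 1.2 | 66% / 81% | 15 | 68% / 79% | 11 |
| 1.5 | 64% / 81% | 17 | 66% / 79% | 13 |
| 1.8 | 62% / 81% | 19 | 64% / 79% | 15 |

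The fall and rise columns differ by little more than Monte Carlo error. The rise is the direction that matters for renal safety.

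**Adding log baseline.** With regression to the mean of 0.2 and baseline log-SD 1.5, the SD of the log ratio is √(0.8² + (0.2 × 1.5)²) = 0.854. Then z = 0.140 / (0.854 × 0.0626) = 2.62 and power is Φ(0.66) = 0.75. Log baseline as covariate brings the SD back to 0.8. In simulation, for a fall: planned 60%, log ratio 75%, log ratio with log baseline 81%. For a rise: 62%, 72%, 79%. The gaps to the covariate model are 21 and 17 points.

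**Range.** At moderate effects the gap to the covariate model runs from about 5 points (rise of 1.198, baseline log-SD 0.8: 89% versus 94%) to about 21. At the extremes of effect size it is smaller. With a log-scale effect of 0.05 in the two-arm setting below, powers are 14% planned and 17% for either log model. At a ratio of 0.80 with 600 per arm, the planned test loses about 1 to 8 points to the log-ratio test.

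**Departures from the model** (two arms, 510 per arm, baseline log-SD 1.2, residual SD 0.8, regression to the mean 0.2; log-scale fall of 0.14 in the first three rows, rise of 0.4 in the last):

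| Setting | Planned | Log ratio | Log ratio + log baseline | Ranks of log ratio |
|---|---|---|---|---|
| Gaussian residuals | 63% | 77% | 81% | 75% |
| t(4) residuals | 76% | 76% | 80% | 85% |
| t(3) residuals | 86% | 76% | 80% | 92% |
| Gaussian, effect only if baseline >30 mg/g | 77% | 59% | 61% | – |

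For a uniform proportional effect, ranking the log ratio beats ranking the absolute change in each setting, by 12, 9 and 6 points. That isolates the scale from the use of ranks. When the effect is confined to high baselines, the absolute scale does better, and ranking the log ratio does not recover the loss.

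**No effect.** The planned test rejects in about 5% to 6% of trials, and the log-scale tests in about 5%.

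**The case against.** The strongest reply is that the power argument is close to circular. Data simulated as log-normal with Gaussian residuals and a uniform proportional effect are the setting in which a log-ratio model is best. The documents never say that UACR behaves this way, and the shift categories are reporting bands that say nothing about error structure. Under t(3) residuals, or an effect only in patients above 30 mg/g at baseline, the planned test wins. This stands. A reader might infer that the plan loses a fixed 14 to 19 points of power, or that a renal signal will probably be missed. The documents support neither. That figure depends on assumed spread, effect and residuals, and it includes the gain from a baseline covariate as well as from the scale.

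The analogy with amylase and lipase is also only partial. Protocol 3.2 explains the interest in those enzymes: their elevations contributed to the monitoring committee's advice to drop 3.0 mg in an earlier study. No such history is given for UACR. The SAP therefore shows that the method is available, not that the sponsor regards it as right for every skewed analyte.

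Consequences are limited. UACR is not a listed endpoint and lies outside the multiplicity scheme. Renal event summaries, eGFR, creatinine and the shift table sit beside it. A reader might also infer that the trial cannot report a percent difference in UACR. That goes too far, because SAP 6.1 allows additional analyses without a revision. The accurate statement is that no such estimate is prespecified.

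None of this answers the missing effect size, or the mixing of baseline level with response in the ranking.

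**Conclusion.** The point holds as a cheap improvement, not as an error that invalidates the analysis. The mixing of baseline with response and the lack of an effect size follow from the method itself. The power gain of roughly 5 to 20 points is conditional on proportional variation, near log-normal errors, a uniform dose effect of moderate size, and about 510 patients per arm. Its size rises with the baseline spread, which the documents do not give, and its sign is not guaranteed outside those conditions. The case for the change therefore rests first on having a prespecified, interpretable estimate and only second on power.

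**What to change.** In SAP 6.10.1.2.9, take UACR out of the shared rank model. Analyse log(postbaseline/baseline) with treatment and log baseline UACR in the model, following the approach in SAP 6.10.4 for amylase and lipase. Report the ratio of geometric means for each higher dose versus 1.5 mg with a 95% CI.

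Keep a rank-based test as supportive, preferably on ranks of the log ratio, which holds up well under heavy tails. If an effect limited to patients with raised baseline UACR is thought plausible, retaining the planned rank test alongside covers that case.

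The cost is about one sentence of SAP text and reuse of existing model code, with no new data. The Protocol leaves room for the exception, since change from baseline to endpoint "will be analyzed using an ANOVA on the ranks with treatment as a fixed effect unless otherwise specified". The downsides are that a substitution rule for values below the assay limit must be written down in advance, and that the result is less directly comparable with rank p-values from earlier dulaglutide studies.

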6.10.1.3. Gastrointestinal Safety

Because certain gastrointestinal (GI) AEs, including nausea, vomiting, and diarrhea, are among the most common events reported in patients treated with dulaglutide, summaries and analyses for incidence will be provided for each randomized treatment to compare the treatment effect on GI tolerability.

The time courses of prevalence, incidence (newly occurring episodes), and onset (first occurrence) of GI AEs (nausea and/or vomiting and/or diarrhea) will be plotted by treatment, regardless of severity, and by severity.

The maximum severity and duration of treatment-emergent nausea and/or vomiting and/or diarrhea through the end of the treatment will be summarized by treatment.

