At Visit 2, the screening laboratory results will be reviewed and definite patient eligibility will be established. During the Lead-In Period, eligible patients should continue their prestudy therapy (metformin, same formulation and dose), in order to allow reliable assessment of HbA1c at baseline (Visit 3). If patients develop a condition that is a contraindication for the use of metformin or initiate other agents that are prohibited between entry (Visit 1) and randomization, they will be considered ineligible and will be discontinued from the trial before randomization. During this period, patients will be trained on disease monitoring and disease management procedures, study diaries, and study procedures.

Study Period II (Treatment Period):*Randomization (Visit 3)*

At Visit 3, patients will perform all required baseline study procedures (including the collection of all baseline laboratory measures) prior to randomization and prior to taking the first dose of study drug. Patients who continue to be eligible will then be randomized in a 1:1:1 ratio to 1 of the treatment arms: (1) dulaglutide 4.5 mg, (2) dulaglutide 3.0 mg, or (3) dulaglutide 1.5 mg. Immediately after randomization, the patient will inject the first dose of study drug at the study site, according to the dose escalation regimen described below. The date and time of the first dose of study drug should be recorded on the electronic case report form (eCRF).

Following randomization, patients will participate in a 52-week Treatment Period.

Postrandomization Treatment Period (end of Visit 3 to Visit 11)

Beginning at randomization, all patients will receive dulaglutide 0.75 mg once weekly for 4 weeks (Weeks 1-4), followed by dulaglutide 1.5 mg once weekly for 4 weeks (Weeks 5-8). At Week 8 the dosing will diverge based on the randomized treatment arm:

- Dulaglutide 1.5 mg arm: Patients will continue to receive dulaglutide 1.5 mg once weekly for the remainder of the treatment period.
- Dulaglutide 3.0 mg arm: Patients will receive dulaglutide 3.0 mg once weekly for the remainder of the treatment period.
- Dulaglutide 4.5 mg arm: Patients will receive dulaglutide 3.0 mg once weekly for 4 weeks (Weeks 9-12), and then escalate to dulaglutide 4.5 mg once weekly for the remainder of the treatment period.

Study Period III (Safety Follow-Up Period):

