10.3.4.4. Gastrointestinal Safety

Because GI AEs, including nausea, vomiting, and diarrhea, are among the most common events reported in patients treated with dulaglutide, summaries and analyses for incidence, time to onset, duration, and severity of nausea and vomiting may be provided for each treatment during the weeks of dose escalation, during the period on the final assigned dose, and overall, to compare the effects of the 3 different doses on GI tolerability, as well as the overall effects of randomized therapies.

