Summary statistics for categorical measures will include number of subjects and percentages. The proportions of patients achieving target HbA1c $<7.0\%$ and $\leq 6.5\%$ at Week 36 (Visit 9) will be analyzed using a longitudinal logistic regression with repeated measurements. In this model, pooled country, treatment, visit, and treatment-by-visit interaction will be fit as fixed effects, and baseline HbA1c as a covariate. A logistic regression model will be applied for the aforementioned HbA1c target analysis at Week 36 (Visit 9) using LOCF by removing visit-related terms from the corresponding longitudinal logistic regression model.

For the analysis of other categorical measures, Fisher's exact test will be used for treatment comparisons unless otherwise specified. Categorical variables will be summarized by sample size and the number of patients and percentages for each treatment group at each visit. Imputed data may be applied in model-based data analyses, but will not be used in data listings. The latter will only present the non-imputed raw data, including site-reported scheduled and unscheduled visits, or early termination visit data; however, only scheduled visits for the measure of interest will be included in the summary table and statistical inference unless otherwise stated.

All statistical analyses will be conducted with SAS Version 9.4® or higher unless otherwise stated.

For primary DBL, all tables, figures, and listings (TFLs) will use the data up to Week 36 (Visit 9) or the study discontinuation date, whichever is earlier, unless otherwise specified.

For the final DBL delivery, TFLs will use the data up to the end of the treatment period (Week 52 [Visit 11]) or the study discontinuation date, whichever is earlier, unless otherwise stated.

Before each DBL, all key data will be reviewed. Any decision to exclude either subjects or observations from the statistical analyses will be made and documented by the study team, and will include the rationale.

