6.10.1. Adverse Events

Summary statistics will be provided for the following data: medical history and/or preexisting condition AEs, TEAEs, treatment-emergent AESIs, and study and/or treatment discontinuations due to AEs or death. The numbers and proportions of patients experiencing each corresponding AE will be reported by treatment.

For each patient, the primary AE analysis will be summarized up to the end of the treatment period or premature termination of the study, whichever comes first.

As supportive analyses, SAEs, TEAEs, and treatment-emergent AESIs for each patient will be summarized through the end of the study, including the Safety Follow-up Period.

The incidence of patients with at least 1 TEAE will be summarized by PT and by treatment group, and also by the SOC and PT.

A summary of TEAEs by maximum severity will be presented descriptively by treatment group.

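### GI incidence is compared by arm over the whole treatment period although doses are identical through Week 8, and no between-arm estimate or test is planned for the period after doses diverge

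*SAP*

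**What the plan says.** Protocol 5.1 describes a common start: "all patients will receive dulaglutide 0.75 mg once weekly for 4 weeks (Weeks 1-4), followed by dulaglutide 1.5 mg once weekly for 4 weeks". Then "At Week 8 the dosing will diverge based on the randomized treatment arm". The 4.5 mg arm takes one further step: "Patients will receive dulaglutide 3.0 mg once weekly for 4 weeks (Weeks 9-12), and then escalate to dulaglutide 4.5 mg once weekly". The 3.0 mg and 4.5 mg arms are therefore also identical through Week 12.

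For GI tolerability, SAP 6.10.1.3 says that "summaries and analyses for incidence will be provided for each randomized treatment to compare the treatment effect on GI tolerability". That sentence names no period. The period comes from SAP 6.10.1, under which "the primary AE analysis will be summarized up to the end of the treatment period or premature termination of the study", and from SAP 6.1, under which outputs for the primary database lock "will use the data up to Week 36 (Visit 9) or the study discontinuation date, whichever is earlier". Severity and duration follow the same window: "The maximum severity and duration of treatment-emergent nausea and/or vomiting and/or diarrhea through the end of the treatment will be summarized by treatment".

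The same SAP section also plots, by treatment and by severity, the time course of prevalence, new episodes and first onset of nausea, vomiting and diarrhea.

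Protocol 10.3.4.4 allows for GI summaries and analyses "during the weeks of dose escalation, during the period on the final assigned dose, and overall". The wording is permissive. It gives two purposes: to compare the three doses, and to show the overall effects of the randomized therapies. The SAP does not take up the split. It gives no reason, and its revision history does not mention it.

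**The concern.** GI events are a known tolerability problem of this drug. Protocol 3.2 lists a higher incidence of GI adverse events among the reasons why the 3.0 mg dose was dropped from an earlier dose-finding study. Protocol 5.5 explains that the escalation scheme was chosen partly to reduce them. How much more GI intolerance 3.0 mg and 4.5 mg cause than 1.5 mg is therefore a central safety question here.

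The planned incidence is of the ever/never kind: a patient counts once if any event occurs in the window. Events in Weeks 1-8 arise under the same doses in every arm, so they add about the same number of cases to each arm and carry no information on the dose contrast. A patient with nausea in Week 2 is already a case and cannot register a further one after escalation. Maximum severity has the same feature, because an early severe event can fix a patient's maximum before the doses differ. A modest overall ratio could then be read as similar tolerability of the doses when part of the similarity comes from the shared start.

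**Working it through.** Neither document gives a GI incidence, an early GI rate or a power figure for GI comparisons, so there is no figure of the plan's to reproduce. The direction of the effect follows from the design. The size has to be illustrated with assumed rates.

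**Inputs from the documents**
- Identical dosing through Week 8 in all arms, and through Week 12 in the 3.0 mg and 4.5 mg arms (Protocol 5.1 and 7.1).
- 600 patients per arm (SAP 5.2).
- Two-sided alpha 0.05, with Fisher's exact test for categorical measures (SAP 6.1).

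**Share of the window with identical dosing**
- All arms: 8/36 = 22.2% at the primary lock and 8/52 = 15.4% at the final lock.
- 4.5 mg against 3.0 mg: 12/36 = 33.3% and 12/52 = 23.1%.

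**Dilution**

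Let p0 be the risk of an event in Weeks 1-8, the same in all arms. Let a (1.5 mg) and b (a higher dose) be the risks of a first event after Week 8.
- Overall risks: p0 + (1 - p0)a and p0 + (1 - p0)b.
- Overall risk difference: (1 - p0)(b - a).
- Overall ratio: [p0 + (1 - p0)b] / [p0 + (1 - p0)a], which is nearer 1 than b/a whenever p0 > 0 and a and b differ.

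Power loss has two sources: the difference is smaller, and both proportions move toward 50% (for the risks used here), which raises the variance.

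**Illustration (assumed a = 8%, b = 14%; difference 6.0 points and ratio 1.75 after Week 8)**

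Power uses the normal approximation for two proportions with n per arm: Φ([d√n - 1.96√(2p̄(1 - p̄))] / √(p1(1 - p1) + p2(1 - p2))), where d = p2 - p1 and p̄ is the mean of p1 and p2. Overall power uses n = 600. Post-Week-8 power uses the event-free patients, n = 600(1 - p0).

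| p0 | Overall risks | Difference (points) | Ratio | Power, overall | Power, after Week 8 (n) |
|---|---|---|---|---|---|
| 2% | 9.8% vs 15.7% | 5.9 | 1.60 | 86.3% | 90.9% (588) |
| 5% | 12.6% vs 18.3% | 5.7 | 1.45 | 78.1% | 90.0% (570) |
| 10% | 17.2% vs 22.6% | 5.4 | 1.31 | 64.9% | 88.4% (540) |
| 20% | 26.4% vs 31.2% | 4.8 | 1.18 | 45.1% | 84.5% (480) |
| 30% | 35.6% vs 39.8% | 4.2 | 1.12 | 32.3% | 79.5% (420) |

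Example row: with p0 = 10%, 0.10 + 0.90 × 0.08 = 17.2% and 0.10 + 0.90 × 0.14 = 22.6%. The difference is 0.90 × 6.0 = 5.4 points.

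With lower later risks (3% vs 6%) and p0 = 10%, the overall risks are 12.7% and 15.4%, the ratio is 1.21 and power is 26.9%. After Week 8 the ratio is 2.0 and power is 66.2% with 540 per arm.

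Fisher's exact test gives slightly lower power throughout. By simulation, the p0 = 10% row of the table becomes about 62% and 87%.

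**What randomization protects**

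Patients still on study drug at Week 8 have been treated identically and blind up to that point, so who remains cannot depend on the assigned dose. That risk set is comparable between arms. From Week 9 the higher-dose arms differ from 1.5 mg, so stopping in Weeks 9-12 can depend on dose, and a risk set formed at Week 12 loses this protection.

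**The case against.** The case on the other side is substantial.

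- **The overall comparison is sound.** It compares the regimens as given, titration included, and Protocol 10.3.4.4 names overall effects as one of its purposes. A reader might infer that the comparison is biased or should be replaced. The documents do not support that: it answers a different question from the dose contrast and should stay.
- **The protocol split is optional.** Leaving it out of the SAP is an unexplained omission, not a breach, and SAP 6.1 allows additional analyses without amendment.
- **Later GI events are not hidden.** A reader might infer that the plan is blind to what happens after escalation. It is not. The time-course plots in SAP 6.10.1.3 would show a divergence after Week 8. Protocol 10.3.5 plans to relate dose or concentration to nausea and vomiting. SAP 6.3 gives Kaplan-Meier curves with a log-rank p-value for treatment discontinuation due to adverse events, though for all such events rather than GI events alone. What remains missing is a planned estimate with an interval, or a test, of GI incidence between arms after the doses differ.
- **The size is assumed.** In absolute terms the loss can be small: 6.0 points become 5.9 at an early risk of 2%, and 5.4 at 10%. The ratio and the power move more. The trial is not sized for GI events, and they are outside the multiplicity-controlled hypotheses in SAP 6.1.4.

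All four points stand. They limit the concern to a missing supplementary analysis but do not remove it.

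**Conclusion.** The point holds as a cheap improvement to the SAP. The direction is certain if identical blinded dosing gives equal early risk across arms: shared events before Week 8 shrink the overall risk difference by (1 - p0) and pull the ratio toward 1. The size cannot be determined from the documents. Under the assumed 8% vs 14%, overall power runs from 86% (p0 = 2%) to 32% (p0 = 30%), against 91% to 80% after Week 8. The illustration also assumes the same later risks for every patient who is event-free at Week 8.

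A reader might go further and conclude that the GI contrast is what the trial is meant to show, or that the plan would make the higher doses look as well tolerated as 1.5 mg. Neither follows. The primary contrast is HbA1c at Week 36, and without GI rates nobody can say whether the dilution would change any conclusion.

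**What to change.** Keep the overall GI analysis in SAP 6.10.1.3 and add the following.

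1. **Main addition, from Week 8.** By arm, each higher dose against 1.5 mg: incidence of nausea, vomiting and diarrhea with onset or worsening from Week 8 onward, with the risk difference, its 95% CI and Fisher's exact test, plus maximum severity over the same period. The denominator is patients still on study drug at Week 8. Unlike the illustration above, it includes patients who had an earlier event.
2. **Counting rule.** An event that began before Week 8 counts if it worsened afterwards, using the logic of the treatment-emergent definition in SAP 6.10 with Week 8 as the reference point. This needs dated severity changes, which the documents do not describe. If severity changes are not dated, count onsets and list separately the events ongoing at Week 8.
3. **From Week 12, descriptive only.** Show the same summaries without a test, next to study drug discontinuations due to GI events in Weeks 9-12, because patients who stopped for intolerance in those weeks have left the risk set. This view is useful because the 4.5 mg arm takes its final dose only from Week 13.
4. **One sentence** on why the SAP departs from, or now takes up, the optional split in Protocol 10.3.4.4.

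Cost: SAP wording and one more table, largely from adverse event and dosing dates already collected. Denominators are slightly smaller, and the analysis is exploratory and not controlled for multiplicity, which the table should state.
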